8.7.4 Primary Analysis

A standard pharmaco-epidemiological inferential analysis will be conducted treating the registry data as a cohort with dynamic exposure to both prophylactic treatment and to COVID-19 infected patients and adjusting for potential confounding.

Both crude and adjusted hazards ratios will be estimated for prophylactic regimens of interest and any observed impact on the risk of infection among HCWs based on all statistical inferential models will be reported.

Outcomes will be adjudicated to exposure time based on prior decision rules agreed with the SAC. Hazards for each subject-week will be compared and adjusted for exposure to prophylaxis over time, exposure to COVID-19 positive patients over time and to other covariates, accounting for subject-level clusters. Repeated time-to-event analyses with competing risk will be carried out.

Handling of missing data and unexplained drop-outs will be discussed with the SAC. Interaction terms to be considered will also be discussed with the SAC and clinicians.

Matching or other balancing methods such as estimated propensity score matching, inverse probability weighting or marginal structural methods, or alternative methods, will be considered to potentially address the identified biases and allow for evaluation of association.

In case the number of infection cases is lower than anticipated to allow for such analyses, matched case-control analyses will also be considered.

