3.1.1.2 Exclusion criteria

- A confirmed SARS-CoV-2 infection or clinically diagnosed COVID-19 prior to the first known exposure to confirmed or clinically diagnosed COVID-19 patient (Index Date).
- Participation in a ‘blinded’ clinical trial, i.e. unaware of exact treatment received as part of the clinical trial.

Date checks to confirm eligibility criteria will be completed for all subjects. Subsequently, healthcare workers that indicate first exposure to COVID-19 infected patients or COVID-19 symptoms/diagnosis/test results prior to 2020 will be dropped from any analysis. Similarly, healthcare workers that are not exposed to COVID-19 infected patients within 30 days following enrolment will be excluded from any analysis.

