 - Other antiparasitics
- Antiretrovirals for Human Immunodeficiency Virus (HIV) (yes/no). If yes, please specify.
 - Lopinavir
 - Ritonavir
 - Tenofovir
 - Nelfinavir
 - Other antiretrovirals
- Antivirals (yes/no). If yes, please specify.
 - Oseltamivir
 - Favipiravir
 - Arbidol
 - Anti-hepatitis C treatments
 - Remdesivir
 - Other antivirals
- Medication for high blood pressure and cardiovascular disease (yes/no). If yes, please specify.
 - Angiotensin-converting enzyme (ACE) inhibitor (e.g. lisinopril, enalapril)
 - Angiotensin II receptor blockers (ARB) inhibitor (e.g. losartan, irbersartan)
 - Other anti-hypertensive for high blood pressure
 - Other medicine for high blood pressure and cardiovascular disease (E.g. antiarrhythmics, inotropes, chronotropes)
- Nonsteroidal Anti-inflammatory Drugs (NSAIDs) E.g. Aspirin, Ibuprofen, Indomethacin, Celecoxib, Diclofenac (yes/no).
- Botanicals-- Artemisia teas (COVID Organics) (yes/no)
- Immunocompromising drugs such as corticosteroids, cancer chemotherapy, cyclosporine, colchicine, drugs for autoimmune conditions such as lupus, rheumatoid arthritis or Crohn's disease (yes/no)
- Changes in concomitant medications

Any prophylactic medications that are indicated as concomitant medications being taken by HCWs will be considered during analysis as part of a prophylactic treatment. This will apply to the following prophylactic medications:

- Hydroxychloroquine
- Chloroquine
- Azithromycin
- Lopinavir/ritonavir
- Ivermectin

4 Data security/privacy

- The Application has received a full penetration test from an accredited third party to cover cyber security threats.
- Data is segregated between the collection nodes and analysis nodes. Only information technology support staff have access to the data in the nodes for the express purposes of server support.
- All data on the analysis platform is tokenized with a unique patient token generated on the node. This tokenization uses a powerful salted hash algorithm (a document explaining this process may be reviewed if necessary but cannot be released for security reasons).
- Access to the data platform is controlled by Azure Active Directory accounts managed by the Parexel Support team.
- Access to the Application can only be achieved by end user registration using a set of industry leading authentication providers.
- The application has a unidirectional data flow from the node to the analysis platform so there is no risk of horizontal escalation issues.

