6.3 Descriptive analyses

Prior to implementing the analysis to address the primary objectives of the study, descriptive analyses will be carried out to understand the main features and patterns in the population and in the data collected. Study population characteristics will be tabulated at index date.

WHO Ordinal Scale for Clinical Improvement (see Appendix 1) scores distribution over time will be displayed. Kaplan-Meier estimates will be calculated, and curves plotted for each time-to-event outcome.

The observed incidence weekly rates of PCR-confirmed or symptomatic COVID-19 and of COVID-19-related hospitalizations and deaths will be tabulated over weeks by facilities and compared according to

prophylactic treatment use (yes/no; by treatment, subject to sufficient sample size; and by pre- and post-exposure (to COVID-19 patients) use, subject to sufficient sample size).

Applications of estimated propensity scores will be employed to explore differences between HCWs' profiles exposed versus non-exposed to potential prophylactic treatments. Propensity scores will be estimated for receipt of potential prophylactic treatments based on key covariates of interest for the HCWs' profiles (age, gender, race, type of HCW, BMI, smoking status, medical history). Estimated propensity score distributions will be displayed over weeks and a concordance analysis performed to detect any trend over time.

Stratified pooled analyses at country level will also be displayed.

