6.3.7 Prophylactic medications

Prophylaxis usage of subjects included in the study will be descriptively summarized for HCWs with and without COVID-19 infection (see Table 8.2.8 in the appendix):

A stacked bar chart will be used to display the prophylaxis usage during the follow-up period. The x-axis will be dates of survey responses and the stacked bars will be grouped by yes/no (corresponding to prophylaxis use at specific dates). This will be done separately for HCWs infected with COVID-19 and those uninfected. The stacked bar charts can be used to compare prophylaxis use among infected/uninfected HCWs over time. This will be done for “any prophylaxis use” and if sample if sample sizes permit they will

be presented for the major individual prophylaxis treatments (ie. azithromycin, chloroquine/hydroxychloroquine, ivermectin, lopanavir).

Prophylaxis usage pre- and post- first date of COVID-19 exposure will also be described, stratified further by COVID-19 infection status.

- Types, intake frequency, and doses of prophylactic treatments
 - Treatment name
 - Date started
 - Date stopped
 - Dose (intake)
 - Duration of treatment
 - Dose frequency and dosing interval
 - Status (stopped/ongoing)
 - Reason for stopping (not available/side effects/expense/other)
 - Number of missed doses and reason (not available/side effects/expense/other)

For HCWs with COVID-19 at entry: prophylaxis treatments used before the COVID-19 infection date will be described.

For HCWs with COVID-19 at follow-up: prophylaxis treatments used over the entire follow-up time available in the data cut. In addition, prophylaxis treatments used within 2 or 4 weeks (TBD) before COVID-19 infection date will be described.

For HCWs with no COVID-19 infection at any time: prophylaxis treatments used over the entire follow-up time available in the data cut. In addition, prophylaxis treatments used within 2 or 4 weeks (TBD) prior to the data cut date will be described.

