6.4 Primary analysis

6.4.1 Frailty model: mixed effect Cox regression

For the time to COVID-19 infection outcome, both crude and adjusted hazards ratios will be estimated for time to COVID-19 infection with respect to prophylaxis use. The primary objective of this analysis is to assess the association between prophylactic treatments and the reduced risk of SARS-CoV-2 infection in HCWs caring for COVID-19 patients. A mixed effect Cox regression model (ie. frailty model) will be used to estimate adjusted hazard ratios. This method will allow the utilization of both the repeated measures gathered from each HCWs surveys, as well as the incorporation of time-varying covariates of interest such as PPE usage and COVID-19 exposure. Each subject will be included as a random effect. Both time-fixed and time-varying covariates will be included in the model. Covariates will be assessed using a univariate model, any covariates with a p-value less than 0.20 will be included in a multivariate model. A backward stepwise process will then be completed, where the covariates with largest p-value are removed one at a time until all covariates that remain are significant at the 0.10 level. The time-fixed covariates, healthcare facility and country will be included in the model regardless of their significance level. Including the healthcare facility and country covariates will make each healthcare worker's COVID-19 outcome conditionally independent on the background COVID-19 incidence occurring within each subject's healthcare facility and country. A list of additional covariates to be considered can be found in Table 5.4.1. For each subject in the control group, the index date (ie. time of first known exposure to COVID-19 patients) will be used as time zero. For HCWs that are treated with prophylaxis at any time their index date will be 7 days after initiation of treatment. Having an index date near treatment initiation will prevent the introduction of survivorship bias into the analysis.

Table 5.4.1 Model Covariates

Time-fixed/Time-varying Covariate	Covariate Name
Time-fixed Covariates	Healthcare facility, Country, Age, Biological Gender, BMI, Smoking status, Ethnicity, Blood type, Primary work location, Type of healthcare worker, Medical history

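### The primary Cox model gives treated and control HCWs different time zeros, so an inert drug can look protective or harmful

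*SAP*

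**What the plan says.** SAP 6.4.1 takes first known exposure to COVID-19 patients as time zero for the control group. For the rest: "For HCWs that are treated with prophylaxis at any time their index date will be 7 days after initiation of treatment". The reason given is: "Having an index date near treatment initiation will prevent the introduction of survivorship bias into the analysis". Prophylaxis is in neither row of the covariate table in 6.4.1. The time-varying row lists household, patient-exposure and PPE items only.

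Protocol 8.7.4 plans something different: "Hazards for each subject-week will be compared and adjusted for exposure to prophylaxis over time". It adds: "Outcomes will be adjudicated to exposure time based on prior decision rules agreed with the SAC". SAP 6.4.1 states no such rules. It does not say what happens to infections before a treated HCW's time zero, or how reported stop dates are used.

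Four other places bear on the point:

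- SAP 3.1.1.2 excludes "A confirmed SARS-CoV-2 infection or clinically diagnosed COVID-19 prior to the first known exposure to confirmed or clinically diagnosed COVID-19 patient (Index Date").
- SAP 3.6.5 widens the treated group: "Any prophylactic medications that are indicated as concomitant medications being taken by HCWs will be considered during analysis as part of a prophylactic treatment".
- SAP 6.3 expects starts on both sides of first exposure, since it compares incidence "by pre- and post-exposure (to COVID-19 patients) use, subject to sufficient sample size".
- SAP 6.3.7 sets a cut-off at infection for a descriptive table: "For HCWs with COVID-19 at entry: prophylaxis treatments used before the COVID-19 infection date will be described". The primary rule has no such cut-off.

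**The concern.** Three routes to bias are open.

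1. **Starts after first exposure.** The rule rightly avoids crediting waiting time to treatment, but it discards that untreated, event-free time altogether. HCWs infected while waiting, who then never start, remain control events. The control rate is inflated and the hazard ratio falls.
2. **Starts more than 7 days before first exposure.** The treated clock runs through time before the Index Date. Eligibility makes that time free of confirmed or clinically diagnosed infection, so it is immortal time. The hazard ratio falls.
3. **Starts after infection.** Nothing limits treatment to use before infection, and listed drugs reported as concomitant medication count. An infected untreated HCW who later reports one leaves the control group, with the infection before the new time zero. The hazard ratio rises.

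This contrast answers the primary objective, and SAP 6.5 carries it into the time-to-event secondary analyses. Under SAP 6.7, a non-significant hazard ratio of 0.8 or less triggers Bayesian borrowing, so a value produced by the rule could lead to further analysis.

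**Working it through.** **Inputs from the documents.** N = 10,000, 20% untreated, 10% risk in the untreated, RR 0.78, 80% power (SAP 5; protocol 8.7.7); two-sided 5% (SAP 6.1); 12 weeks of follow-up (SAP 3.4).

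**Assumptions.** True hazard ratio 1; constant hazard from the Index Date; follow-up to week 12 after it; no covariates or frailty. Start-date patterns are assumed because the documents give none.

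**The plan's own figure.** Expected events are 2,000 × 0.10 + 8,000 × 0.078 = 824. Power by Schoenfeld's formula is Φ(√(824 × 0.2 × 0.8) × |ln 0.78| − 1.96) = Φ(11.48 × 0.2485 − 1.96) = Φ(0.89) = 81%. The stated 80% reproduces, so 0.78 is a fair yardstick.

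**Common quantities.** Weekly hazard λ = −ln(0.9)/12 = 0.00878. Mean time at risk is 0.10/λ = 11.39 weeks. The 2,000 controls give 200 infections in 22,779 weeks.

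**Route 1.** Let late starters begin uniformly over weeks 0–8 and never start if infected first; the other users' clocks coincide with the controls'.

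- P(infected before start) = 1 − (1 − e^(−8λ))/(8λ) = 0.0343.
- Mean time each late starter adds to the controls = ∫₀⁸ tλe^(−λt)(1 − t/8)dt = 0.0904 weeks.
- The treated rate stays at λ.

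| Late starters | Control infections | Control weeks | Control rate | Ratio |
|---|---|---|---|---|
| 5% (400) | 213.7 | 22,815 | 0.00937 | 0.94 |
| 10% (800) | 227.4 | 22,851 | 0.00995 | 0.88 |
| 25% (2,000) | 268.6 | 22,960 | 0.01170 | 0.75 |

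**Route 2.** If every user starts uniformly over the w weeks before exposure, the mean pre-exposure time on the treated clock is (w − 1)²/(2w). That is 1.125 weeks for w = 4 and 3.06 for w = 8. The ratio is about 11.39/(11.39 + 1.125) = 0.91 and 11.39/(11.39 + 3.06) = 0.79.

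**Route 3.** A share p of infected controls leaves, and mean infection time is 5.89 weeks. Control infections are 200(1 − p) and control weeks 22,779 − 200p × 5.89. For p = 10%, 25% and 50% the control rates are 180/22,661, 150/22,484 and 100/22,189. The ratios are 1.11, 1.32 and 1.95.

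**Cox fits to simulated null data (N = 10,000, 80% intended users).**

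| Pattern | HR under the SAP rule |
|---|---|
| All users start 7 days before exposure | 1.00 |
| 5%, 10%, 25% late starters; infected first never start | 0.94, 0.88, 0.75 |
| Same; half of those infected first still start | 0.97, 0.94, 0.86 |
| Same; all of them still start | 1.00 |
| All users start over the prior 4 or 8 weeks | 0.90, 0.73 |
| Only 25% of users start over the prior 8 weeks | 0.93 |
| 10%, 25%, 50% of infected untreated later report a listed drug; infections dropped | 1.11, 1.33, 1.95 |
| Same; infections counted as treated events at time zero | 1.14, 1.41, 2.19 |
| Same, dropped, plus 25% late starters | 0.83, 0.98, 1.45 |
| Extreme: every user starts over weeks 0–4 or 0–8 after exposure | 0.54, 0.36 |

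For 5%, 10% and 25% late starters, a false benefit at p < 0.05 appeared in roughly 10%, 40% and nearly all runs. In the 8-week case of route 2, Cox gives a lower value than the rate ratio because treated time beyond week 12 on the shifted clock has no controls at risk.

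**Hazard shape.** The neutral cases need a constant hazard. If all users start on the exposure day and only the 7-day shift operates, a Weibull hazard falling since exposure (shape 0.5) gives 0.74 and a rising one (shape 2) gives 1.19.

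**Common origin at the Index Date, exposure switched on at start + 7 days.** The hazard ratio was 0.99 to 1.01 throughout.

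**The case against.** The SAP never says outright that prophylaxis is coded ever/never. That is so. It is an inference from the group wording and from the table. But a time-varying term on one clock would make two time zeros unnecessary, so the text needs settling either way.

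The shift does remove the usual immortal time for starts after exposure. This also stands: there the survivorship sentence is incomplete, and it is plainly wrong only for starts more than 7 days before exposure. As a general claim of prevention it does not hold.

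The upward route is the least grounded. The concomitant section covers medication other than for COVID-19, and protocol 6 describes prophylaxis as use to prevent infection, so a drug taken to treat COVID-19 belongs in neither section. What remains is misreporting, unrelated prescriptions and prophylaxis begun after infection. The ratios are close to 1/(1 − p), so they mostly reflect the assumed share. The gap in the rule is real; its frequency is unknown.

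The largest ratios need every user to start after exposure, whereas the protocol aims for about 75% of enrollees on prophylaxis. The moderate rows carry the point. Concomitant drugs are asked about weekly, so a start during follow-up can be placed within a survey interval. Drugs reported only there and already in use at enrollment have no listed start date.

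Other planned analyses do not help. The subgroup and sensitivity analyses in SAP 6.6 and 6.7 state no other time zero. The weighting that SAP 7.1 and 7.5 place in section 5.4.2 has no corresponding section.

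**Conclusion.** The concern holds. As written, the rule can bias the primary hazard ratio in either direction for an inert drug, and it departs without explanation from the subject-week comparison in protocol 8.7.4. Under moderate assumptions the null estimate runs from 0.75 (25% late starters) to 1.33 (25% of infected untreated HCWs later reporting a listed drug); the lower end is beyond the design effect of 0.78. It is about 1.0 when the clocks coincide and the hazard is constant, or when opposing biases happen to cancel. Direction and size cannot be known in advance. These figures do not model enrollment delay, calendar changes in incidence, facility and country adjustment, or frailty. This must be fixed before the primary analysis is programmed.

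**What to change.** - Use the Index Date as time origin for every HCW, with no risk time before it.
- Enter prophylaxis as time-varying: unexposed until a pre-specified lag after the reported start (the 7 days can stay), exposed afterwards. Earlier person-time and infections count as unexposed. A start after infection then cannot change the group.
- Pre-specify how reported stop dates are handled, and a dating rule for drugs counted only through the concomitant-medication section.
- Delete the survivorship-bias sentence. If the current rule is kept at all, make it a sensitivity analysis and state how infections before time zero are treated.
- Weighting or marginal structural methods, which protocol 8.7.4 allows, can be added. This change does not by itself address survival from the Index Date to enrollment.

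The cost is SAP wording and programming. Prophylaxis start and stop dates are already collected, and a weekly counting-process data set is already needed for PPE and patient exposure. No new data are required.

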Pneumonia	X	X	-
Nausea or vomiting	X	X	-
Headache or migraine	X	X	-
Abdominal pain (pain in tummy)	X	X	-
Asthenia (weakness or loss of strength)	X	X	-
Arthralgia (joint pain)	X	X	-
Anosmia (loss of smell)	X	X	-
Ageusia (loss of taste)	X	X	-
Blue coloring in toes	X	X	-
Diarrhea (two or more looser-than-normal stools in 24 hours)	X	X	-
SARS-CoV-2 testing			
Tested? (yes/no)	X	X	-
Type of test	X	X	-
PCR (positive/negative)	X	X	-
Antigen test (positive/negative)	X	X	-
Serology (IgG and/ or IgM, positive/negative or titer)	X	X	-
Date of test	X	X	-
Serology testing	X	X	-
Household history (COVID-19)			
Number of household contacts	X	X	-
Additional household member(s) exposed to COVID-19 (yes/no) If yes, how many?	X	X	-
Additional household member(s) with symptoms consistent with COVID-19 (yes/no) If yes, how many?	X	X	-
Additional household member(s) diagnosed with COVID-19 (yes/no) If yes, how many?	X	X	-
Underlying conditions and key morbidities			
Chronic lung disease	X	-	-
Diabetes mellitus	X	-	-
Cardiovascular (heart) disease	X	-	-
Chronic renal (kidney) disease	X	-	-
Chronic liver disease	X	-	-
Immunocompromised condition (HIV/AIDS, organ transplant, other)	X	-	-
Tuberculosis	X	-	-
Neurologic/neurodevelopmental	X	-	-
Hypertension (high blood pressure)	X	-	-
History of stroke	X	-	-
Other chronic diseases	X	-	-
If female, currently pregnant	X	-	-
If female, currently breastfeeding/lactating	X	-	-
Job characteristics			
Type of healthcare work	X	-	-

Primary work location (ED, ICU, Medical floor)	X	X	-
Number of hours with patients	X	X	-
Concomitant medications (other than for COVID-19)			
Antibiotics (yes/no)	X	X	-
Antimalarials (yes/no)	X	X	-
Antiparasitics (yes/no)	X	X	-
Antiretrovirals for HIV (yes/no)	X	X	-
Antivirals (yes/no)	X	X	-
Medication for high blood pressure and cardiovascular disease (yes/no)	X	X	-
Nonsteroidal Anti-inflammatory Drugs (NSAIDs) (yes/no)	X	X	-
Botanicals (yes/no)	X	X	-
Immunocompromising drugs (yes/no)	X	X	-
COVID-19 vaccine (to be selected as applicable)			
Convidicea (Ad5-nCoV)	X	X	
CoronaVac (Sinovac)	X	X	
Covaxin (BBV152)	X	X	
EpiVacCorona (Vector Institute)	X	X	
Janssen Pharmaceuticals (Johnson & Johnson) (Ad26.COV2.S)	X	X	
Moderna COVID-19 Vaccine	X	X	
Novavax (NVX-CoV2373)	X	X	
Oxford-AstraZeneca COVID-19 Vaccine	X	X	
Pfizer-BioNTech COVID-19 Vaccine	X	X	
Sinopharm BBIBP-CorV	X	X	
Sputnik V COVID-19 Vaccine	X	X	
Other (please specify)	X	X	

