3.6.4 Personal Protective Equipment Use

- At enrollment
 - Type and use of PPE (yes always, yes not always, no) prior to enrollment
- Weekly follow-up
 - Type and use of PPE (yes always, yes not always, no) at time of confirmed exposure(s) in the past week
 - Number of COVID-19 exposures in the absence of a mask
 - Longest COVID-19 exposure in the absence of a mask

Details on the following types of PPE will be captured:

- Mask (type of mask—N95 respirator mask, other)
- Eye protection/goggles/face shield
- Gown
- Gloves

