5 Determination of Sample Size

The targeted sample size of approximately 10,000 HCWs assumes that 20% of the study population are non-exposed to potential prophylactic treatments, with a baseline risk of SARS-CoV-2 infection in the study period of 10% (for unexposed: not treated with potential prophylactic treatment). A total of N=10,000 allows for 80% power to identify an effect size of Relative Risk = 0.78.

If these sample sizes are not reached with respect the study population being exposed/non-exposed to potential prophylactic treatments, the relative risk may be detected with lower power or it may not be statistically significant. However, the secondary objectives can still be examined.

6 Statistical analysis

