6.1 Overview

All statistical analyses will be conducted using R (version 1.3.1093), unless otherwise specified.

For all descriptive analyses, categorical variables will be summarized by number of observations and percentage (%). Percentages will be rounded to one decimal place and will be based on available observations (known values), unless otherwise specified. Continuous variables will be summarized using descriptive statistics (n, mean, with standard deviation; minimum, first quartile, median, third quartile,

and maximum). Outliers will be included in descriptions as part of presenting ranges and percentiles (25th and 75th). The mean and SD will be rounded to one decimal place.

All statistical tests will be two-sided and at 5% level of significance.

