6.3.4 Exposure to COVID-19 patients

The following household characteristics of subjects included in the study will be descriptively summarized for HCWs with and without COVID-19 infection (see Table 8.2.5 in the appendix):

- Contact with confirmed COVID-19 patients (Yes; No)
- Direct care to COVID-19 patients (Yes; No)
- Face-to-face contact (within 1 metre) of COVID-19 patients (Yes; No)

- Present when aerosol generating procedures performed (Yes; No)
- Average number of COVID-19 patients in contact each week for past month
- Number of days spent at work in last week
- Number of hours worked directly with COVID-19 patients in last week

For HCWs with COVID-19 at entry: responses to the baseline survey will be used.

For HCWs with COVID-19 at follow-up: maximum responses over the entire follow-up time available in the data cut. In addition, maximum responses in the 2 or 4 weeks (TBD) prior to COVID-19 infection date will be described.

For HCWs with no COVID-19 infection at any time: maximum responses over the entire follow-up time available in the data cut. In addition, maximum responses in the 2 or 4 weeks (TBD) prior to the data cut date will be described.

Maximum responses will be defined as:

- For a yes/no question, “yes” will be considered
- For number of days spent at work and number of hours worked directly with the COVID-19 patients, a summation will be done
- For average number of COVID-19 patients in contact each week for past month, an average will be calculated

Using the follow-up survey data for questions with yes/no responses, the following plot will be generated to display exposure over time:

For,

i = question #

n_{it} = # of yes answers to question i at time t

n_t = # of responders at time t

$$r_t = \sum_i n_{it}/n_t$$

A line plot of r over time will then be displayed. Two separate lines will be generated, one for HCWs infected with COVID-19 and another for HCWs that were never infected with COVID-19.

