Time-varying Covariates	Others in household exposed to COVID-19 infected individuals, Others in household showing symptoms of COVID-19, Others in household diagnosed with COVID-19, Number of COVID-19 infected patients exposed to, Direct care to COVID-19 patients, Face-to-face contact of COVID-19 patients, Present when aerosol generating procedures performed, Mask usage, Gown usage, Eye protection usage, Glove usage
-------------------------	--

Note: The necessity to create composite variables or collapse categories within variables will be determined upon the completion of the descriptive analyses. A correlation analysis will be completed to assess the level of correlation between variables, if a high level of correlation is found only one of the variables will be included as a covariate in the models.

A Cox model with mixed effects can be formulated as $h_i(t) = h_0(t) \exp(\mathbf{X}_i B + \alpha_j)$, where α_j denotes the random effect associated with the j -th cluster. The random effect can be thought of as a random intercept that modifies the linear predictor, while the shared frailty term has a multiplicative effect on the baseline hazard function: $h_i(t) = h_0(t) \exp(\alpha_j) \exp(\mathbf{X}_j B)^3$.

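### SAP Table 5.4.1 leaves four collected exposure-intensity measures off the candidate covariates: number of unmasked exposures, longest unmasked exposure, hours with COVID-19 patients, and days worked

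*SAP*

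**What the plan says.** **Model.** SAP 6.4.1 specifies a mixed-effect Cox model with time-fixed and time-varying covariates. Facility and country are forced in. Every other covariate comes from Table 5.4.1, is screened at p < 0.20 and is then eliminated backward at 0.10. The table's time-varying row holds three household items, "Number of COVID-19 infected patients exposed to, Direct care to COVID-19 patients, Face-to-face contact of COVID-19 patients, Present when aerosol generating procedures performed", and use of mask, gown, eye protection and gloves. Its time-fixed row ends with "Primary work location, Type of healthcare worker, Medical history". A note under the table allows composites and collapsed categories after the descriptive work, and keeps only one of any highly correlated variables.

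**Collected but not listed.** SAP 3.6.4 has, at weekly follow-up, "Number of COVID-19 exposures in the absence of a mask" and the longest such exposure. SAP 3.6.3 has days worked in the past week. SAP 6.3.4 describes days at work and "Number of hours worked directly with COVID-19 patients in last week".

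**Protocol.** Section 8.7.1 leaves it to the SAP to define variables for intensity of exposure to infected patients over time. Section 8.7.4 says that subject-week hazards will be adjusted for exposure to COVID-19 positive patients over time.

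**Work location.** Protocol Appendix 2 schedules "Primary work location (ED, ICU, Medical floor") at enrolment and weekly. Protocol Table 1 marks job characteristics at enrolment only.

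**The concern.** In this registry the decision to take prophylaxis is not random, and both documents acknowledge confounding by indication. Workload and unprotected contact are plausible drivers of both prophylaxis use and infection. If they differ between users and non-users beyond what the listed covariates capture, the adjusted hazard ratio keeps confounding that data already in hand could reduce.

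A secondary objective is touched as well. SAP 6.5 tests risk factors only among covariates that survive into the final primary model. A measure that is never a candidate cannot be tested there, although the objective names PPE and COVID-19 exposure.

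**Working it through.** **1. Collected against listed.**

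| Measure | Where collected | In Table 5.4.1 | Other SAP analysis |
|---|---|---|---|
| Unmasked exposures, number | Weekly: protocol 8.3.4, Appendix 2; SAP 3.6.4 | No | None described; not in the PPE summary (6.3.8) |
| Unmasked exposure, longest | Same | No | None described |
| Days worked | Weekly: protocol 8.3.3, Appendix 2; SAP 3.6.3 | No | Descriptive (6.3.4) |
| Hours with patients | Appendix 2: enrolment and weekly; SAP 6.3.4 sums them over surveys | No | Descriptive (6.3.4) |
| Patient count | Weekly | Time-varying | Descriptive |
| Direct care, face-to-face, aerosol procedures | Enrolment and weekly | Time-varying | Descriptive |
| Mask use (always / not always / no) | Enrolment and weekly | Time-varying | Descriptive |
| Primary work location | Appendix 2: weekly; Table 1: enrolment only | Time-fixed | Shell table of static variables |

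**2. What the listed terms already carry.** Appendix 2 asks the unmasked items only when mask use is not always or no. Weekly mask use therefore already flags any week with unmasked exposure. What is missing is the number and duration within those weeks: one brief lapse and many long contacts share a category. Patient count is itself an intensity measure, but it does not record time spent.

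**3. Whether another analysis fills the gap.** The propensity score in SAP 6.3 uses age, gender, race, type of worker, BMI, smoking and medical history, with no exposure term. SAP 7.1 and 7.5 point to an inverse probability weighting section numbered 5.4.2, but the primary-analysis section contains only 6.4.1. No described analysis adjusts for the four items.

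**4. Why no size is given.** For an omitted binary factor, the multiplicative bias in the hazard ratio is approximately

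(1 + a(h − 1)) / (1 + b(h − 1)),

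where a and b are its prevalence among users and non-users and h its hazard ratio, all conditional on the listed covariates. The documents give none of the three. If a = b or h = 1, the factor is 1. Its direction depends on the sign of a − b, which is also unknown.

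**5. Room in the model.** Inputs from SAP section 5: N = 10,000, a calculation that "assumes that 20% of the study population are non-exposed to potential prophylactic treatments" (2,000 unexposed, 8,000 exposed), "with a baseline risk of SARS-CoV-2 infection in the study period of 10" per cent, and relative risk 0.78. From SAP 6.1: "All statistical tests will be two-sided and at 5% level of significance".

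- Expected events: 2,000 × 0.10 + 8,000 × 0.078 = 200 + 624 = 824.
- The plan's 80% power: with 0.78 read as a hazard ratio, Schoenfeld's formula gives Φ(|ln 0.78| × √(824 × 0.2 × 0.8) − 1.96) = Φ(0.248 × 11.48 − 1.96) = Φ(0.89) = 81.4%, close to the stated 80%. A two-proportion test gives 87.7%. This point does not dispute the figure and uses only the event count.
- Four linear terms: 824 / 4 = 206 events per added parameter. One composite: 824. Total events per parameter cannot be given, because the number of facilities is not stated.

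**6. Collection schedule for work location and hours.** Appendix 2 has both weekly. Table 1 has job characteristics, the heading that covers both, at enrolment only. SAP 3.6 says all its variables are collected weekly, but that sentence also covers blood type and demographics at entry, so it is weak evidence. SAP shell Table 8.2.3 treats work location as static. The hours item refers to patients in general in Appendix 2 and to COVID-19 patients in SAP 6.3.4.

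**The case against.** The strongest reply is that the model already adjusts for exposure. Table 5.4.1 has a time-varying patient count, the three WHO exposure questions and four PPE items. Protocol 8.7.1 ties its definitions to the depth of data actually collected. The table is a list to be considered, and its note leaves composites open. Most of this stands: the protocol's request is partly met, and the residual may be small. But the note names none of the four items, and nothing in the SAP provides for adding unlisted ones.

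The second reply is practical. The unmasked items are structurally blank in always-masked weeks. Appendix 2 does not collect them, or days worked, at enrolment, while time zero for controls may be earlier. Days and hours can fall because a worker is already becoming ill. Forcing several workload terms in could also clash with the collinearity rule. These points shape the fix but do not defeat it: blanks can be coded zero, terms lagged and a composite used. The listed weekly patient count is likewise not collected at enrolment in Appendix 2.

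A reader might infer more than the documents support:

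- *That the omitted items are the most direct measures of risk.* Patient count, aerosol procedures and mask use are direct too, and are listed.
- *That the gap can be sized by treating any unmasked week as an unadjusted factor.* Mask use already marks such weeks, so that calculation measures something else.
- *That listing the items would remove the confounding.* At best it would reduce it, and p-value selection could drop them again.
- *That work location is wrongly frozen although updated weekly.* The documents conflict on whether it is.

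**Conclusion.** The concern holds as a gap in the candidate list. Four collected measures of exposure intensity are not considered for adjustment in the primary model, no other described analysis uses them for adjustment, and the protocol left exposure intensity over time to the SAP.

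The consequence is possible residual confounding by indication, of unknown direction and size. It may be small or material, and no magnitude should be quoted. Confounding from this source requires that the items differ between prophylaxis users and non-users, and predict infection, after the listed covariates are taken into account. The documents neither show nor exclude that. On work location and hours, the supportable conclusion is that the passages must be reconciled.

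**What to change.** 1. Add the four items to the time-varying row of Table 5.4.1, or add one intensity composite built from them and defined before outcomes are examined.
2. Lag the terms by at least one survey week, so that reduced work caused by early illness is not read as low exposure.
3. Code both unmasked items as zero in weeks when a mask was always worn.
4. Keep the intensity term or terms in the adjusted model regardless of p-value. If the SAP's correlation check shows high collinearity, use the composite rather than dropping items.
5. State that the items are unavailable for risk time before enrolment, and how that person-time is handled.
6. Reconcile protocol Table 1, protocol Appendix 2, SAP 3.6 and SAP shell Table 8.2.3 on the collection of work location and hours, and settle whether hours means all patients or COVID-19 patients. If work location was in fact collected weekly, model it as time-varying.

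**Cost.** This is a SAP edit with no new data collection. It adds one to four parameters (more if terms are categorised or work location becomes time-varying) against about 824 events under the design assumptions. Some early person-time will lack values: that before enrolment and, because of the lag, the first follow-up week for items not asked at entry.
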